	3- Time elapsed till final restoration performed	Stopwatch	Continuous outcome measured in minutes

(S) Study design: Randomized controlled.

(T) Time of follow up:6 months.

8. Trial design:

Randomized controlled trial (R.C.T).

III. Methods

A) Participants, interventions & outcomes:

9. Study settings:

This study will be carried out on patients attending the out-patient clinic in Pediatric Dentistry and Dental Public Health Department-faculty of Dentistry, Cairo University, Egypt.

The procedure will be carried out by postgraduate student [name], B.D.S(2014)-Pharos University in Alexandria (PUA) and without an assistant.

10. Eligibility criteria:

Inclusion criteria:

- Children:

- 1- Aged 4 to 7, in good general health and medically free.
- 2- Cooperative patients who will comply to follow ups.
- 3- Parents provided with written informed consent.

- Teeth:

- 1- Bilaterally Carious vital primary molars with reversible pulpitis.
- 2- Restorable teeth with no more than 1/3 of root resorption.

Exclusion criteria:

- Children:

- 1- Children with medical, physical, or mental conditions.
- 2- Unable to attend follow up visits.

- Teeth:

- 1- Primary molars with any congenital anomalies.
- 2- Previously accessed teeth.
- 3- At operative procedure, haemorrhage control is unachievable after pulpotomy.

11. Interventions

The principal investigator will carry out all treatment procedures, using the split mouth technique, meaning that both groups (I & II) will be in the same patient.

For both interventions:

1. Informed consent from participating parents.
2. Baseline records photographs, percussion test, periapical radiograph, and personal data collection (Appendix 1: Diagnostic chart).
3. Allocation (concealed by withdrawing a sealed opaque envelope containing eight times folded paper containing the type of dressing material that will be used then writing patient name and ID on it and will be opened after performing the access cavity).
4. Diagnostic chart with personal, medical, and dental history will be filled (Appendix 1: Diagnostic chart).
5. Clinical examination will be performed to assess the clinical inclusion criteria. (Pulpal and periapical diagnosis is established after clinical examination).
6. Preoperative and Postoperative photographs will be taken.

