7. The radiographic examination will be performed by taking periapical x-ray using (parallel technique) through machine to assess the inclusion criteria. The preoperative radiograph will serve as a reference for the follow-up radiographs. Standardization of the technique to avoid any distortion in the vertical dimension and to provide reproducible images using x-ray holding device.
8. Preoperative and postoperative radiograph will be taken by parallel technique using XCP film holder (Super Bite, Hawe Neos Dental SA, Switzerland).
9. Administration of inferior alveolar nerve block (Septodont, Scandonest® 2% L Mepivacaine HCl. 2% and Levonordefrin 1:20,000 Injection, U.S.P.) at the side of the affected tooth.
10. Application of rubber dam for isolation, then a standardized pulpotomy procedure will be performed using a large sterile round end bur in a high-speed handpiece with copious irrigation, a sharp spoon excavator will remove pulpal tissues to the orifice level. Hemostasis will be achieved by the application of a wet cotton pellet to achieve complete hemostasis.
11. Children will then be allocated into either one of the groups alternatively depending on the pulpotomy medicament used as follows:
Group I (Experimental group) collagen based pulpotomy.
Group II (Control group) Biodentine pulpotomy.

Group I (Experimental group) collagen based Pulpotomy:

1. Collagen based pulpotomy will be applied (sterile medicated collagen particles, Biofil-AB, Eucare Pharmaceuticals Pvt. Ltd, Chennai, India) according to the manufacturer's instructions and gently placed over the pulp stumps to a thickness of 2 mm.

Group II (Control group) Biodentine pulpotomy:

1. Biodentine (Septodont, Saint-Maur-des-Fossés, France) will be applied according to the manufacturer's instructions and placed over the radicular pulp with the help of a suitable sterile amalgam carrier. Gentle condensation of the mix will be done in the pulp chamber with a moistened cotton pellet.

12. For both groups;

The rest of the pulp chamber will be filled with glass ionomer cement.

Tooth will then be restored with stainless steel crown (3M ESPE, St Paul, MN, U.S.A.).

12. Outcomes:

Primary outcome:

Absence of periapical radiolucency and internal/ external root resorption (Binary outcome detected with periapical x-ray by Parallel technique using XCP film holder (Super Bite, Hawe Neos DentalSA, Switzerland).

Secondary outcome:

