1- Survival rate (absence of any complication or complementary treatment) in terms of:

1-Absence of spontaneous pain. (Binary outcome measured with direct questioning to the patient).

2-Absence of swelling. (Binary outcome measured visually by intraoral/extraoral examination).

2- Time elapsed till final restoration performed.

13. Participant timeline:

Patients will be diagnosed to determine whether they are eligible for the inclusion criteria of this study or not.

Eligible patients will then start their treatment on the same visit.

	STUDY PERIOD					
	Enrolment	Allocation	Treatment visit	Post-treatment	Close-out	
TIMEPOINT	-t1	0	0	T1 (3m)	T2 (6m)	
ENROLMENT:						
Eligibility screen and patient selection	X					
Informed consent from participating pts	X					
Allocation (concealed in closed white envelop)	X					
INTERVENTIONS:						
The pulpotomy procedure (gaining access to the pulp)		X				
Allocation of the patient to one of the treatments groups (open the closed white envelope)		X				
Application of pulp dressing material (collagen and Biodentine)			X			
Final restoration			X			
ASSESSMENTS:						
baseline variables	1- photographs	X		X	X	X
	2- percussion test	X		X	X	X

	3- preoperative periapical radiograph	X				
	4- personal data	X				
outcome variables	Calculation of time-elapsed till final restoration			X		
	Questioning the patient about the absence of spontaneous pain	X			X	X
	Visual examination of patient to check the absence of sinus or Swelling	X			X	X
	Periapical radiograph to check the absence of periapical radiolucency, internal/ external root resorption	X		X	X	X

14. Sample size:

Sample size will be calculated.

15. Recruitment:

Patients attending the out-patient clinic in the pediatric dentistry department- Cairo University, having bilateral carious lower molars will be carefully assessed for eligibility to participate in our study by one of the main investigators [name], then a full explanation of the nature of our experiment and the importance of maintaining this primary tooth and restoring it for proper functions and the drawbacks of extracting it. Full mouth treatment will be offered for them.

B) Assignment of interventions:

16. Allocation:

16a. Random sequence generation (Randomization):

Teeth that will be included in the current trial will be randomly assigned one of the experimental groups using closed white envelopes (simple randomization 1:1 ratio).

a) Sequence generation:

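### Pain is asked of the child, but the split-mouth comparison is between teeth, and the protocol sets no way to assign a pain report to a material

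*Protocol*

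**What the plan says.** **Design.** Section 11 says the investigator will work "using the split mouth technique, meaning that both groups (I & II) will be in the same patient". Section 16a agrees: "Teeth that will be included in the current trial will be randomly assigned one of the experimental groups". Section 15 recruits children with carious lower molars on both sides, and the section 13 timeline has one treatment visit that lists both dressings. Item 11 of section 11 says otherwise: "Children will then be allocated into either one of the groups alternatively depending on the pulpotomy medicament used". A row of the section 13 timeline likewise allocates the patient to one of the groups.

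**Pain.** Section 12 lists spontaneous pain first under survival, as a "Binary outcome measured with direct questioning to the patient". Section 13 schedules "Questioning the patient about the absence of spontaneous pain" at enrolment, 3 months and 6 months. Neither place mentions a side or a tooth. The inclusion criterion for the children who answer is "Aged 4 to 7, in good general health and medically free".

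**Recording.** Section 19 calls for a separate diagnostic chart for each patient. The form in Appendix 1 has one field for the tested material, one for the participating tooth and one column for spontaneous pain. Section 18 includes palpation and percussion at 3 and 6 months, but section 12 does not use either to define or locate pain.

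**Other teeth.** Section 15 adds: "Full mouth treatment will be offered for them".

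**The concern.** Teeth are compared, but pain is asked of the child. Swelling and radiographic findings carry their own location. A child's yes to a question about pain does not, unless someone asks where and writes it down. In a split-mouth trial that yes could refer to the collagen tooth, the Biodentine tooth, both, or a tooth outside the study.

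Pain is the only patient-reported component of clinical success, and the aim in section 7 covers clinical as well as radiographic success. If reports are spread over both teeth, the pain comparison moves towards no difference. That is also what the null hypothesis in section 7 states, so a measurement fault could be read as a finding.

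A statistical analysis plan cannot repair this later, because it cannot recover a side that was never asked about or recorded.

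**Working it through.** The protocol gives no sample size, power or pain rate, so there is no figure to reproduce. The check is how the pain difference behaves under different ways of crediting a report.

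**Inputs from the protocol:** two study teeth per child, one per material (section 11); a yes/no pain outcome from questioning the child (sections 12 and 13); no attribution rule.

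**Assumptions, not in the documents:** true pain rates pB = 5% (Biodentine) and pC = 15% (collagen), chosen for illustration only; independent teeth; two-sided alpha 0.05; 80% power.

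**Correct tooth-level record**
- Pain in the collagen tooth only: 0.15 × 0.95 = 0.1425
- Pain in the Biodentine tooth only: 0.05 × 0.85 = 0.0425
- Both: 0.05 × 0.15 = 0.0075
- Difference: 0.1425 − 0.0425 = 0.10
- Child with any pain: 0.1425 + 0.0425 + 0.0075 = 0.1925

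**(a) Every answer credited to both teeth.** Each arm shows 19.25%. The difference is 0 and the risk ratio 1.0, whatever the true rates.

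**(b) A share u of one-sided reports cannot be localised and is credited to both teeth.** Both one-sided cells are multiplied by (1−u), so observed difference = (1−u) × true difference. At u = 0.5: 0.07125 − 0.02125 = 0.05.

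**(c) A share m of one-sided reports is credited to the wrong side, regardless of material.** The observed cells are (1−m)(0.1425) + m(0.0425) and (1−m)(0.0425) + m(0.1425), so observed difference = (1−2m) × true difference. At m = 0.20: 0.1225 − 0.0625 = 0.06.

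Pairs needed use the McNemar formula, with D the sum of the two one-sided cells and d their difference: n = [1.96√D + 0.842√(D − d²)]² / d². For the correct record, D = 0.185 and d = 0.10, giving 143.

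| Crediting of reports | Difference (points) | Risk ratio | Pairs for 80% power |
|---|---|---|---|
| Correct by tooth | 10 | 3.0 | 143 |
| Wrong side, m = 0.10 | 8 | 2.33 | 225 |
| Wrong side, m = 0.20 | 6 | 1.86 | 401 |
| Wrong side, m = 0.30 | 4 | 1.50 | 906 |
| Half not localised, credited to both | 5 | 1.41 | 289 |
| All credited to both | 0 | 1.0 | none suffices |

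Other assumed rates give the same proportional shrinkage. At m = 0.20, 2% v 10% falls from 8 to 4.8 points and 10% v 30% from 20 to 12.

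**When there is no loss.** If each side is asked about and localised correctly, u = 0 and m = 0 and the difference is intact.

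**When the direction is open.** Case (c) needs error that ignores the material. Section 17 says blinding is not possible and then that participants and outcome assessors will be blinded. If either knows the material, reports could be steered to one tooth and the difference could be inflated, reduced or reversed.

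**The case against.** The strongest reply is that the protocol is silent here rather than wrong. It does not give the wording or number of the questions, so side may well be asked. The two teeth are on opposite sides, which makes a side-specific question feasible. The chart names a tooth and a material, so two charts per child would give each pain entry a tooth. Swelling and the radiographs can be tied to a tooth without any of this. If item 11 of section 11 governs and each child receives one material, the problem between materials disappears.

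Most of this stands, and it rules out several stronger readings that a reader might infer:
- That the child is asked only one question. The text does not say so.
- That pain can never be assigned to a material. It could be; what is missing is the means.
- That the pain difference is zero by construction. This follows only if one answer is credited to both teeth, which no section states.
- That the clinical objective cannot be answered. Survival also covers swelling and the absence of other complications or further treatment.
- That non-study teeth create a false difference. The offer of full mouth treatment does not say that other teeth need care, and pain credited to both study teeth adds concordant pairs only.

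The reply does not remove the mismatch. Followed as written, one chart per patient with one pain column gives one answer for two teeth. No section calls for a second chart or for a question about side. Split-mouth is also the better supported reading of the design, given sections 11 (opening), 15 and 16a.

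**Conclusion.** The point holds as a gap in measurement: under the split-mouth design, the protocol sets no way to assign a child's pain report to a material. The effect on the pain difference ranges from none, if reports are localised correctly, to complete loss, if every answer is credited to both teeth. With random side errors, 80%, 60% or 40% of the true difference remains at m = 0.10, 0.20 or 0.30. These values of m and u and the pain rates are assumptions.

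A shift towards no difference is the likely result only if reports are credited to both teeth or the errors ignore the material. Given the contradiction on blinding in section 17, the opposite direction cannot be excluded.

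The damage is limited to a secondary component of survival in sections 7 and 12 (Appendix 1 labels the clinical assessment primary). The radiographic primary outcome is recorded by tooth and is not affected. The point depends on the split-mouth statement, so the conflict with item 11 of section 11 must be reconciled as well. It should be corrected before data collection, because the missing side cannot be recovered afterwards.

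**What to change.** - **Sections 12 and 13:** define spontaneous pain as a tooth-level outcome. At each scheduled visit, ask child and parent about the left and right sides separately, and have the child point.
- **Section 19 and Appendix 1:** complete one chart, or one row, per study tooth, with the pain entry tied to that tooth.
- **Percussion:** the scheduled test may support localisation but should not be required before spontaneous pain is counted, since tenderness on tapping is a different thing.
- **Pain that cannot be localised, or that comes from a non-study tooth:** report it per child as its own category. Add a sensitivity analysis that counts non-localised pain against both study teeth. This changes the pain rates and the risk ratio but adds only concordant pairs, so it cannot restore lost information on the difference.
- **Sections 11, 13 and 16a:** reconcile whether children or teeth are allocated.
- **Section 17:** reconcile the statements on blinding.

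The cost is a few extra questions at visits that already take place and a second chart or row per child. Some reports will remain unassignable and will have to be shown separately.

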Pulpotomy is considered the gold standard procedure for treating cariously exposed pulps in asymptomatic primary teeth. Which is based on the healing ability of the radicular pulp tissue following amputation of the infected coronal pulp. (5)

Mineral trioxide aggregate (MTA) has been recommended as the gold standard for vital pulp therapy; however, it has some disadvantages, such as long setting time, poor handling properties, high cost, and the potential for tooth discoloration. Biodentine (Septodont, Saint-Maur-des-Fossés, France), one of the new-generation, bioactive endodontic cements, has been claimed to have improved properties over MTA.

Biodentine presents high biocompatibility with the dental pulp, it has high antibacterial effects and antifungal activity, has a shorter setting time than MTA as a result of the calcium chloride in the liquid component of Biodentine. It also has higher flexural strength, compressive strength and modulus of elasticity than MTA. Consequently, Biodentine can be used as a pulp dressing as well as a base material. (6)

Quest is on for newer pulpal medicaments that are biocompatible and capable of healing the dental pulp by producing reparative dentin and/or dentinal bridge in response to various stimuli and surgical exposure.

Collagen has a proven rate of success in the field of dentistry as guided tissue regeneration, root conditioning, hemostatic, and wound dressing agent. It has inherent properties like low immune response and toxicity, ability to promote cellular growth and attachment, homeostasis, and added advantage of antibiotic incorporation. (7)

7. Objectives:

Aim of the study

To assess clinical and radiographic success after collagen based pulpotomy versus Biodentine pulpotomy in children with cariously exposed vital primary molars.

Hypothesis:

Null hypothesis: No added benefits will be gained from the collagen based pulpotomy clinically and radiographically.

PICO approach:

P: Population: Children 4-7 years with carious vital primary molars.

I: Intervention: Sterile medicated Collagen particles.

C: Control: Biodentine.

O: Outcome:

Outcome		Method of measurement	Unit
1ry outcome: Clinical success	1- Absence of internal root resorption	Periapical X-ray (parallel technique)	Binary
2ry outcome:	1- Absence of pain	Questioning the patient	Binary
	2- Absence of swelling	Visually by intraoral and extraoral examination	Binary

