By shuffling the envelopes then selecting envelop for each patient upon their enrolment.

b) Allocation Concealment:

Using 8-time folded paper on which dressing material was written contained in the closed white envelope.

c) Implementation:

When a patient agrees to participate in the trial, an envelope will be drawn by one of the residents present at the clinic and name, telephone number and patient's ID will be written on it. Those selected envelopes will be opened at treatment visit after performing pulpotomy to choose which material should be used.

Randomization and allocation concealment will be performed by the co-supervisor to avoid selection bias.

17. Blinding:

The blinding is not possible (unfortunately) due to the nature of the trial.

Trial participants, outcome assessors and statistician will be blinded.

C)Data collection, management, and analysis:

18. Data collection methods

Baseline data collection

Plans for assessment and collection of outcomes will be at 3 and 6 months clinically (using visual examination, palpation, and percussion test with back of the mirror) and 0 and 6 months radiographically (using periapical radiograph) and will be done by two blinded assessors independently, and differences will be solved by consensus. To promote data quality, duplicate measurements by the same examiner (intra-examiner agreement) and training of assessors (inter-examiner agreement) will be done.

19. Data management:

Data will be recorded on a diagnostic chart for each patient separately and will be stored with follow up periapical radiographs.

20. Statistical methods:

Clinical and radiographic outcomes will be submitted for statistical analysis by the Statistical Package for Social Science (SPSS) program windows version 13. Results will be calculated using risk reduction (R.R.).

D) Data monitoring:

21. Monitoring

The study work results will be monitored regularly by the supervisors who will have full access to these interim results make the final decision to terminate the trial.

22. Harms

- **Bur breakage:** the bur will be replaced by a new one and treatment will be proceeded.
- **Perforation of pulpal wall or floor:** The tooth condition and size of perforation will be assessed whether the treatment will be to repair the perforation and treatment will be proceeded (the tooth will be removed from the trial) or the tooth will be extracted, and space maintainer will be performed

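### Sinus is scheduled as an outcome check but is missing from the clinical endpoint and the chart, so a tooth whose only clinical sign is a sinus can be scored a clinical success

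*Protocol*

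**What the plan says.** Five parts of the Protocol bear on which clinical signs count.

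- **Section 13 (Participant timeline).** Under the outcome variables, one row reads "Visual examination of patient to check the absence of sinus or Swelling", marked at enrolment, 3 months and 6 months. Percussion ("2- percussion test") is marked at enrolment, the treatment visit, 3 months and 6 months, but it sits under the baseline variables.
- **Section 12 (Outcomes).** The clinical endpoint is headed "Survival rate (absence of any complication or complementary treatment) in terms of" and then lists two items: "1-Absence of spontaneous pain" and "2-Absence of swelling. (Binary outcome measured visually by intraoral/extraoral examination". Neither sinus nor percussion is named.
- **Section 7 (PICO table).** The clinical rows are pain and swelling, with swelling assessed "Visually by intraoral and extraoral examination". There is no row for sinus or percussion.
- **Section 18 (Data collection methods).** Clinical outcomes at 3 and 6 months are collected "using visual examination, palpation, and percussion test with back of the mirror".
- **Appendix 1 (chart).** The follow-up columns are numbered 1 to 5: spontaneous pain, swelling, internal resorption, external resorption and periapical radiolucency. A last column gives an overall success or failure, with no rule for combining the others. Section 19 makes this chart the place of record.

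**The concern.** The schedule tells the assessors to look for a sinus as an outcome, while the endpoint definition and the chart give that finding no role. Two things are at stake. First, a tooth can be counted as surviving although a scheduled outcome check was positive, under a heading that speaks of freedom from complications. Second, a sign with no field on the chart cannot be recovered later: a statistical analysis plan can redefine a composite only from items that were recorded. The same recording gap affects percussion, although no section makes percussion tenderness a component of success.

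**Working it through.** The protocol gives no event rates, sample size or power to reproduce here, so the check is a comparison of the sections.

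**Step 1. Which signs does each place name?**

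| Place | Pain | Swelling | Sinus | Percussion |
|---|---|---|---|---|
| Section 7, PICO table | yes | yes | no | no |
| Section 12, endpoint items | yes | yes | no | no |
| Section 13, outcome variables | yes | yes | yes | no (under baseline variables, but marked at every visit) |
| Section 18, examination methods | not named | not named (visual examination) | not named (visual examination) | yes |
| Appendix 1, follow-up columns | yes | yes | no | no |

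The chart's columns run from 1 to 5 without a gap, so a sinus column lost in text extraction is unlikely.

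**Step 2. How would a tooth with a sinus be scored on the two items in Section 12?**

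| Findings at the visit | Two clinical items | Radiographic outcome |
|---|---|---|
| Sinus only | both met: can be scored as survival | not failed |
| Sinus and spontaneous pain | failed | depends on the film |
| Sinus and swelling | failed | depends on the film |
| Sinus and a radiographic finding | both met: can be scored as survival | failed |

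The exposed teeth are therefore those with a sinus but neither pain nor swelling. Those with a radiographic finding still fail the separate radiographic outcome, which Section 12 makes primary. At 6 months both Section 13 and Section 18 plan a film. At 3 months the film is less sure: Section 13 marks one, whereas Section 18 plans radiographs at 0 and 6 months only.

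**Step 3. Is there anywhere else to record the sign?** No. Section 19 sends the data to the Appendix 1 chart, which has no field for sinus, percussion or palpation. Section 11 lists percussion among the baseline records and points to the same chart, which has no percussion field for baseline either.

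**Step 4. Direction of the effect.** Let f be the true clinical failure rate in an arm, and k the share of those failures whose only clinical sign is a sinus. If such teeth are scored as successes,

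recorded failure = f × (1 − k).

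Recorded failure can only be lower than or equal to f, so clinical success is overstated or unchanged. The protocol gives neither f nor k, so no figure follows from it.

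**The case against.** Four arguments limit the point.

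**The heading may already cover a sinus.** Section 12 opens with "Survival rate (absence of any complication or complementary treatment) in terms of". An assessor could treat a sinus as a complication and enter failure in the chart's last column, which has no stated rule. A reader might infer that the protocol requires every tooth with a sinus to be scored a success. It does not, so only *can be scored* is supported. The heading does not remove the problem, because its closing words confine it to the two listed items. Nor does reading swelling to include a sinus, because Section 13 names the two signs separately.

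**Other routes to failure exist.** Pain, swelling, a radiographic finding or complementary treatment would still mark the tooth. This stands, and it confines the point to teeth with no other failure sign, or to the clinical outcome alone where the film is abnormal.

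**Percussion is a weaker case.** A reader might infer that percussion tenderness was also meant as a success component and was dropped. The documents do not support this: Section 13 lists it under baseline variables, and Section 18 names it only as an examination method. What stands is that a test done at each follow-up has nowhere to be written. Nor can it be said that examiner-observed signs are set aside in favour of the child's report, since swelling is itself observed by the examiner.

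**The bias cannot be sized.** A reader might infer a known distortion of the treatment comparison. Suppose, purely as an assumption, true failure of 10% against 5%. With k = 25% in both arms the recorded rates are 7.5% and 3.75%; with k = 50% they are 5% and 2.5%. The difference falls from 5 to 3.75 or 2.5 percentage points, but the ratio stays at 10/5 = 7.5/3.75 = 5/2.5 = 2. Section 20 reports results as a risk reduction abbreviated R.R., which does not say whether the absolute or the relative measure is meant. These figures only restate their assumptions, and unequal k would change the ratio as well.

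**Conclusion.** The inconsistency is real and is internal to the protocol. Sinus is an outcome check in Section 13 but is absent from the Section 12 components, the PICO table and the chart. As written, a tooth whose only clinical sign is a sinus meets both listed criteria, can be scored a clinical success, and leaves no record of the sign. The conclusion rests on reading the two items in Section 12 as the full list, which its wording favours but the unexplained final column of the chart does not enforce.

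The effect is on the clinical outcome, which Section 12 makes secondary and Appendix 1 labels primary. *Clinical success* is used here for the pain-and-swelling composite that Section 12 calls survival; the PICO table attaches the label "1ry outcome: Clinical success" to a radiographic item. The direction is towards overstated clinical success. The size is unknown and probably small if few failures show a sinus alone, but the protocol gives no rate from which to judge that. The point should be settled before the first follow-up visit, because the sign cannot be reconstructed afterwards.

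**What to change.** - In Section 12 and the Section 7 PICO table, change the swelling component to absence of swelling or sinus, and state that the presence of either one fails the component.
- In Appendix 1, add a sinus cell per tooth at 3 and 6 months, counted in the clinical outcome, and state the rule by which the final success or failure entry follows from the columns.
- In Appendix 1, add a percussion cell per tooth and report the result descriptively by arm. It need not become a component of success.
- Check that Sections 7, 12, 13 and 18 and Appendix 1 then name the same signs.

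The cost is two chart columns and a few words in the outcome definition. The sinus check and percussion are already scheduled, so no examination is added. The downside is that clinical success rates may come out slightly lower.
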